- Chorioamnionitis
- Endometritis within 2 weeks after delivery,
- Postpartum hemorrhage (EBL>1000cc /and or drop in HCT by 10 points) **Neonatal outcomes:**
- Apgar score <7 at 5 min
- Cord Arterial blood pH <7
- Base excess >12mmol/l
- NICU admission within 2 weeks after delivery
- Antibiotic use within 2 weeks after delivery

Exploratory research questions (exploratory endpoints)

There is paucity of clinical data in the literature obtained through well designed clinical trials for Dilapan-S[®] use for cervical ripening in women undergoing induction of labor. We would like to collect following information for assessing safety of Dilapan-S[®] use when compared to Misoprostol. Similar information was collected by Saad et al. [12] in their recent randomized trial comparing efficacy of Dilapan-S[®] to Foley catheter for cervical ripening. These are known potential complications of planned interventions and include (but are not limited to) the following:

Undesirable side effects

- Fever, nausea, vomiting and diarrhea
- Uterine tachysystole
- Hyperstimulation
- Uterine hypertonus
- Failed induction of labor, arrest of first and second stage of labor

Complications specific to dilator insertion

- Vaginal bleeding
- Rupture of membranes
- Cervical laceration
- Excessive pain causing need for analgesia during cervical ripening
- Vasovagal reaction during insertion of the device
- Entrapment of the device
- Fragmentation of device during removal or insertion
- Retraction of device into uterine cavity.

Study subjects inclusion criteria

- 1. Women undergoing labor induction with a gestation of ≥37 weeks determined by best clinical and/or ultrasound estimation
- 2. Live fetus with in cephalic presentation
- 3. Singleton pregnancy
- 4. Able to provide informed consent for participation in the study.

Study subjects exclusion criteria

- 1. Contraindication for vaginal delivery
- 2. Age less than 18 years
- 3. Prior uterine scar from a cesarean section or myomectomy
- 4. Patients who have HELLP syndrome or eclampsia
- 5. Active genital herpes at the time of labor induction
- 6. Complex medical problems that may require assistance with second stage of labor
- 7. Bishop score ≥ 6
- 8. Major fetal congenital anomalies (as assessed by investigator)
- 9. Premature rupture of membranes

Pre-randomization training

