# 3.2. SECONDARY OUTCOMES

Individual and composite maternal and fetal outcomes including overall vaginal delivery rate, cesarean section rate, Bishop score after cervical ripening, infections, postpartum hemorrhage. Neonatal outcomes include Apgar scores, NICU admission and sepsis.

Secondary endpoints are:

- Overall vaginal delivery rate in each group
- Rate of caesarean deliveries in each group
- Rate of operative deliveries (vaginal plus caesarean)
- Bishop score at 12 hours after the intervention and change in Bishop score
- Percentage of subjects who did not receive all 6 misoprostol doses
- Percentage of subjects with failed Dilapan-S insertion
- Percentage of subjects delivering vaginally in 24 hours after the initiation of intervention

- Delivery time
- Initiation of cervical ripening to delivery time
- Initiation of oxytocin to delivery time
- Total length of hospital stay
- Maternal outcomes:
  - Chorioamnionitis
  - Endometritis within 2 weeks after delivery
  - Postpartum haemorrhage (EBL>1000cc and/or drop in HCT by 10 points)
  - 3rd and 4th degree lacerations
- Neonatal outcomes:
  - Apgar score <7 at 5 min
  - Cord arterial blood pH and Cord arterial blood pH <7
  - Cord arterial blood base excess and Cord arterial blood base excess > -12mmol/l
  - NICU admission within 2 weeks after study intervention
  - Antibiotic use within 2 weeks after study intervention

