#### 7.3. ANALYSIS OF SECONDARY ENDPOINTS

All quantitative secondary variables will be summarized separately for each arm. Means of the two treatment arms will be compared with two-sample t-test and Wilcoxon rank-sum test as appropriate.

All secondary variables involving rates and percentages, will be calculated for both arms. Difference in proportions will be derived together with a 95% two-sided confidence interval. The difference between treatment groups will be concluded if the confidence interval does not include zero.

Maternal and neonatal outcomes will be summarized as reported in the CRF.

Delivery time will be presented using Kaplan-Meier curves with censoring for caesarean delivery.

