#### Efficacy data

Table	14.2.1	Summary of Delivery Characteristics
Table	14.2.2.1	Primary analysis for proportion of Vaginal Delivery within 36 hours
Table	14.2.2.2	Analysis for proportion of Vaginal Delivery within 24 hours
Table	14.2.3.1	Analysis for proportion of Mode of Delivery
Table	14.2.3.2	Analysis of Delivery Time
Table	14.2.4.1	Analysis of Bishop score
Table	14.2.5.1	Analysis of Total Length of Hospital Stay
Table	14.2.6.1	Summary statistics of Maternal Outcomes
Table	14.2.7.1	Summary statistics of Neonatal outcomes

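### The cut-off for cord base excess differs between protocol and SAP, and neither version as printed picks out acidotic newborns

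*SAP*

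**What the plan says.** The protocol's list of neonatal outcomes, under the secondary endpoints, gives "Cord Arterial blood pH <7" and then "Base excess >12mmol/l". SAP section 3.2 gives "Cord arterial blood pH and Cord arterial blood pH <7" and then "Cord arterial blood base excess and Cord arterial blood base excess > -12mmol/l". In both lists the preceding item is a 5-minute Apgar score below 7. Neither document states a sign convention for base excess or mentions base deficit, and no footnote or table title corrects the cut-off.

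On analysis, SAP section 7.3 says "Maternal and neonatal outcomes will be summarized as reported in the CRF", and the protocol's section on evaluating the secondary variables says the same. Section 7.3 also has a general rule for secondary rates: a difference in proportions with a two-sided 95% confidence interval, and "The difference between treatment groups will be concluded if the confidence interval does not include zero". In the SAP's list of efficacy tables, Table 14.2.7.1 is titled "Summary statistics of Neonatal outcomes", whereas other secondary tables carry titles such as "Analysis of Bishop score".

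**The concern.** Base excess is a signed quantity, and metabolic acidosis drives it strongly negative. The two neighbouring items each define an adverse tail, and in the SAP the pH and base-excess lines have the same form: the continuous value, then its dichotomy. The base-excess dichotomy should therefore be the acidotic tail, and in neither document is it so as printed. The two documents also disagree with each other. They use the same inequality with opposite signs, so every value above -12 and up to +12 is an event under the SAP and a non-event under the protocol.

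A programmer who codes the SAP literally would fill the base-excess row of Table 14.2.7.1 with non-acidotic newborns and leave out the acidotic ones. If the two arms were then compared, the arm with more acidosis would show the lower rate. The protocol's rationale for the trial includes whether the two methods have similar safety, and neonatal acidosis is part of that.

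**Working it through.** The plan gives no figure for this item, so there is nothing to reproduce. There are three checks.

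**1. The rules side by side.** The third rule is the one implied by the neighbouring pH item.

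| Base excess (mmol/l) | Protocol, > 12 read literally | SAP, > -12 | Acidotic tail, < -12 |
|---|---|---|---|
| -13 | no | no | yes |
| -5 | no | yes | no |
| 0 | no | yes | no |

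Except at exactly -12, the SAP event is the complement of the acidotic tail. If the protocol's label is read as base deficit, > 12 gives the same events as base excess < -12; only the label is then wrong.

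**2. Size, by illustration.** The documents give no distribution of base excess. I assume it is normal with mean m from -2 to -6 and SD s from 2 to 4 mmol/l. Then P(BE < -12) = Φ((-12 - m)/s), P(BE > -12) = 1 - Φ((-12 - m)/s) and P(BE > 12) = 1 - Φ((12 - m)/s).

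- m = -6, s = 4: z = (-12 + 6)/4 = -1.5. The tail is 0.0668 and the SAP rule gives 0.9332. Of the combinations considered, this has the largest tail.
- m = -4, s = 3: z = (-12 + 4)/3 = -2.67. The tail is 0.0038 and the SAP rule gives 0.9962.
- m = -2, s = 2: z = (-12 + 2)/2 = -5. The tail is 2.9 × 10⁻⁷ and the SAP rule gives 0.9999997.
- The protocol rule read literally is largest at m = -2, s = 4: z = (12 + 2)/4 = 3.5, giving 0.00023.

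The protocol's Study Design section plans 153 assessable women per arm, all with singleton pregnancies. Per 153 newborns with a cord gas, the SAP rule gives 153 × 0.9332 = 142.8 up to 153.0 cases. The acidotic tail gives 0.0 up to 153 × 0.0668 = 10.2. At m = -4, s = 3 the counts are 152.4 and 0.6. The number who will have a cord gas is not stated, so the counts only show scale.

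**3. Effect on a comparison, if one were made.** Let p_D and p_M be the true acidosis rates on Dilapan-S and misoprostol. Under the SAP rule the rates become 1 - p_D and 1 - p_M, and

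(1 - p_D) - (1 - p_M) = -(p_D - p_M).

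Each variance term p(1 - p)/n is unchanged when p is replaced by 1 - p. The difference therefore keeps its size and standard error and reverses its sign. Whether the interval includes zero does not change; the arm that appears worse does.

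**The case against.** The authors may have meant one event and written it badly twice. Both documents use the number 12, the SAP's minus sign suggests that negative values were expected, and > -12 may be shorthand for more negative than -12. A minus sign lost when the PDF was read could explain the protocol's version. The intended direction is in any case inferred from the neighbouring items and the usual sign convention; neither document states it.

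The printed inequality may also never be coded. Neonatal outcomes are to be summarised as the CRF reports them, and the CRF is not among the documents; it might hold a tick-box or a deficit. Even if the rule is coded literally, check 3 shows that the decision on whether an interval excludes zero is preserved. The percentages rest on an assumed distribution, and cord gases taken only in selected births could fall outside it.

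Most of this stands as a limit on the consequence. None of it repairs the text. Restoring a lost minus sign in the protocol gives > -12, which is still reversed. Nothing in the SAP signals the shorthand reading, and the same line lists base excess as a continuous value, so a literal program would count the complement. The rule table in check 1 needs no distribution.

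**Conclusion.** The definition is wrong as printed in the SAP and inconsistent with the protocol, whose own version is wrong in either sign and direction or in label. That the documents differ is plain from the text. That the SAP inequality is reversed rests on the sign convention of base excess and on the adverse direction of the adjacent Apgar and pH items.

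Under the assumed distributions, a literal SAP program would flag 93.3% to over 99.99% of newborns with a cord gas, where the acidotic tail holds under 0.001% to 6.7%.

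The severity is minor. The item is probably descriptive only, and a rate above 90% next to the continuous summary would reveal the mistake. If values are recorded, it can be re-derived. The primary endpoint, the 10% margin and the sample size do not depend on it.

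**What to change.** State one definition in the protocol's neonatal outcomes and in SAP section 3.2: cord arterial base excess < -12 mmol/l, equivalently base deficit > 12 mmol/l. Confirm that the CRF field and the program for Table 14.2.7.1 use that sign convention. Keep the continuous summary. If neonatal outcomes are to be summarised only, say so in SAP section 7.3, so that the general confidence-interval rule for rates is not applied to them.

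The cost is one line in each document and a check of the CRF and program. The continuous endpoint in section 3.2 suggests that the value itself is recorded; if so, no new data are needed.

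A separate small item can be settled in the same edit, though the conclusion above does not rest on it. The SAP counts its two-week windows for NICU admission and antibiotics from the intervention, and the follow-up call from enrolment; the protocol counts all three from delivery. These should be reconciled.

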# 3.3. SAFETY ENDPOINTS

### 3.3.1. UNDESIRABLE SIDE EFFECTS

- Fever, nausea, vomiting and diarrhoea
- Uterine tachysystole
- Hyperstimulation
- Uterine hypertonus
- Failed induction of labor, arrest of first and second stage of labor
- Abnormal fetal heart tracing during cervical ripening
- Intrapartum fever

# 3.3.2. COMPLICATIONS SPECIFIC TO DILATOR INSERTION

- Vaginal bleeding
- Rupture of membranes
- Cervical laceration
- Excessive pain causing need for analgesia during cervical ripening
- Vasovagal reaction during insertion of the device
- Entrapment of the device
- Fragmentation of device during removal or insertion
- Retraction of device into uterine cavity.
- Failure to insert Dilapan-S®

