Non-inferiority unblinded randomized controlled trial where subjects will be randomized in a ratio of 1:1 to Dilapan-S[®] and misoprostol groups. We decided to use the non-inferiority design as Misoprostol is considered as one of the accepted and standard treatments for induction of labor in United States. Our assumptions for the trial are based on results of PROBAAT-II trial, a large well designed randomized trial conducted in EU for studying efficacy of mechanical and pharmacological methods for labor induction. Assuming a rate of vaginal delivery within 36 hours to be 65% for Misoprostol and 71% for mechanical method (based on data on transcervical Foley catheter in PROBAAT-II [3] and a recent trial comparing Foley catheter to Dilapan-S[®] for cervical ripening done by Saad et al. [12]), with a non-inferiority margin of 10 % and an expected screen failures rate of 5%, a total of 322 subjects will need to be randomized in ratio 1:1 to Dilapan-S[®] vs Misoprostol group. 153 eligible and assessable subjects are needed in Dilapan-S[®] group and 153 in Misoprostol group for analysis. The study is powered at 85% for detecting the primary outcome with a type 1 error at 2.5% for one-sided test.

Objective for the trial

To assess efficacy of cervical ripening with Dilapan-S[®] or Misoprostol in women undergoing induction of labor.

Primary research question (primary endpoint)

Proportion of subjects achieving vaginal delivery within 36 hours after the initiation of the cervical ripening in Misoprostol and Dilapan-S[®] group.

Rationale: The authors of PROBAAT-II study make the valid point that as an outcome of labor induction, giving birth vaginally is more important than how quickly it happens; therefore 24 hours may not be a long enough time for appropriate assessment. Indeed, the effect found in the PROBAAT-II study would have been reversed had the outcome been measured by assessing vaginal delivery within 36 hours. There is therefore a call to standardize the outcome measure in IOL trials to a vaginal delivery within 36 hours [6], particularly when mechanical methods are employed.

Secondary research questions (secondary endpoints)

- Bishop score at 12 hours after the intervention
- Percentage of subjects delivering vaginally in 24 hours after the initiation of intervention
- Overall vaginal delivery rate in each group
- Rate of operative deliveries
- Rate of cesarean deliveries in each group.
- Total length of hospital stay

Maternal outcomes:

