- 1. Onset of spontaneous labor (defined as regular painful uterine contractions with a dilation of ≥ 4 cm and effacement of 75% or more)
- 2. Vaginal bleeding
- 3. Persistent Category 2 or Category 3 fetal heart tracing
- 4. Spontaneous rupture of membranes
- 5. Spontaneous expulsion of Dilapan-S[®] rods (*if Bishop score is still <6, another set of rods may be placed and allowed to remain in situ for a maximum of 12 hours cumulative based on clinical assessment made by the supervising provider*)
- 6. AROM is indicated

Labor Induction

Subjects in both groups will have an assessment of Bishop score 12 hours after the study intervention and evaluated for amniotomy and Oxytocin infusion. Oxytocin will be initiated as per the institutional guidelines. Amniotomy will be undertaken as soon as clinically feasible. If after 24 hours of amniotomy with Oxytocin the patient is not in active labor [cervical dilatation<6 cm], a diagnosis of failed induction will be made [Appendix 2] and a decision will be made to proceed with cesarean section. During labor, decision to proceed with operative delivery or cesarean section will be made by the attending physician supervising the care of the patient. All subjects will have the option to receive epidural during labor for pain management.

COLUMBIA UNIVERSITY College of Physicians and Surgeons

Oxytocin administration CUMC:

Oxytocin will be administered for labor induction and augmentation as per the institutional guidelines [Appendix 2]. Oxytocin is supplied to L&D unit in prepared bags with 30 units of Oxytocin in 500 cc of Normal Saline. Oxytocin will be initiated at 1 milliunit/minute and increased every 15 minutes, till an optimal response is obtained.

The maximum dose is limited to 40 milliunits/minute.

UTMB:

Oxytocin will be administered for labor induction and augmentation as per the institutional guidelines [Appendix 3]. Oxytocin is supplied to L&D unit in prepared bags with 20 units of Oxytocin in 1000 cc of Lactated Ringers. Oxytocin will be initiated at 2 milliunit/minute and increased every 20 minutes, till an optimal response is obtained. The maximum dose is limited to 40 milliunits/minute.

Delivery period

Data for date, time and mode of delivery and intra-partum complications (incl. those found during induction period) will be collected. The complications will include, but are not limited to following:

- Uterine tachysystole (defined as > 5 contractions per 10 minutes averaged over 30 minutes.

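### Four safety events that either arm can have are classified as specific to dilator insertion, so the plan does not secure the comparison with misoprostol that it promises

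*SAP*

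**What the plan says.** SAP 3.3 splits the safety endpoints into undesirable side effects (3.3.1, Table 14.3.1) and complications specific to dilator insertion (3.3.2, Table 14.3.2). Section 3.3.2 has nine items. The Protocol's list under its exploratory research questions has eight, because the SAP adds failure to insert. Both include vaginal bleeding, rupture of membranes, cervical laceration and "Excessive pain causing need for analgesia during cervical ripening".

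The Protocol introduces its side-effect and dilator lists together and gives their purpose as comparative: "We would like to collect following information for assessing safety of Dilapan-S[®] use when compared to Misoprostol".

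The Protocol's Pre-induction section lists reasons for examining any participant before 12 hours. Vaginal bleeding is one and "Spontaneous rupture of membranes" is another.

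SAP 7.4 draws the safety variables from adverse event and device deficiency reports and presents case counts and patient proportions. It plans no interval or test. Neither document states, for these items, which arms are scored, over what window, with what denominator, or whether attribution to the device is required.

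**The concern.** Entrapment, fragmentation or retraction of a rod needs a rod. Bleeding, membrane rupture, laceration and pain needing analgesia do not. Placing them under a device-specific title tells the person who scores or programs the table that a case must arise from the dilator. The trial is open-label, so that judgement is made with the allocation known.

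The descriptive safety comparison is at stake. The Protocol's rationale asks whether Dilapan-S has a safety profile similar to that of misoprostol, and its Potential Benefits section mentions a safety profile suitable for outpatient use. Unequal counting of common ripening events would distort the published proportions on that question, and one-arm reporting would leave it unanswered for these events.

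**Working it through.** **Which items need a device?**

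| SAP 3.3.2 item | Needs a dilator? | Basis in the documents |
|---|---|---|
| Vaginal bleeding | No | Early-exam reason for all participants (Protocol, Pre-induction) |
| Rupture of membranes | No | Spontaneous rupture is an early-exam reason for all participants; prior rupture is an exclusion criterion |
| Cervical laceration | No | Wording names no device and sets no window; women in both arms labour and deliver |
| Analgesia for pain in ripening | No | Wording refers to the ripening period, which both arms have; the misoprostol arm's section foresees painful contractions |
| Vasovagal reaction, entrapment, fragmentation, retraction, failed insertion | Yes | Wording names the device or its insertion |

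So four of nine SAP items (four of eight in the Protocol) do not fit their heading.

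**Is equal counting secured elsewhere?**

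- The Protocol's Delivery period section collects induction-period complications without restriction by arm. It names tachysystole, hyperstimulation, hypertonus, failed induction or arrest, and intrapartum fever, but none of the four. The list is open-ended, so it permits their capture without requiring it.
- The Protocol's adverse event definition covers any subject and needs no causal link. Its relatedness categories, however, refer only to the study device.
- The Safety population includes women who received at least one misoprostol dose. No text ties Table 14.3.2 to both treatment groups.

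**What each reading would give.**

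1. Table 14.3.2 covers Dilapan-S only: no comparison on the four items.
2. Both arms are shown and the title is applied as a criterion: a misoprostol event cannot qualify, while the same event under Dilapan-S can.
3. Both arms are scored alike: the comparison is sound, but the title is wrong and the window is still missing.

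Each reading calls for an edit.

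**Illustration of reading 2.** The plan gives no figure for these items. The only planned number needed is the arm size. The Protocol says "a total of 322 subjects will need to be randomized in ratio 1:1", so 322 / 2 = 161 per arm. This agrees with its 153 evaluable women per arm and 5% allowance: 153 / 0.95 = 161.05.

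Let p be the true event rate, the same in both arms, and let a_D and a_M be the shares of true events counted under Dilapan-S and misoprostol. Then:

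displayed difference = p × (a_D − a_M)

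Equal counting (a_D = a_M) gives 0. The limit of reading 2 is a_D = 1 and a_M = 0, which gives a difference of p:

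| Assumed p | Expected Dilapan-S cases (161 × p) | Misoprostol cases shown | Displayed difference |
|---|---|---|---|
| 1% | 1.6 | 0 | 1 point |
| 5% | 8.1 | 0 | 5 points |
| 10% | 16.1 | 0 | 10 points |
| 20% | 32.2 | 0 | 20 points |

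The rates are assumptions. The table uses all randomised women; the Safety population may be smaller.

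**The case against.** The strongest reply is that the heading is only a category label. The Protocol describes the listed events as complications of the planned interventions, in the plural. Adverse events are defined for any subject, misoprostol women are in the Safety population, and bleeding and membrane rupture prompt an examination in either arm. The Protocol's instruction not to send device-unrelated events to the funder concerns notification, not data collection. Grouping is also defensible: the Potential Risks section lists bleeding, membrane rupture and laceration beside rod entrapment and retraction, and one table of harms of the newer device is a reasonable display. These endpoints are exploratory.

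Much of this stands, and it defeats two stronger inferences.

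- A reader might infer that misoprostol women cannot be scored, so that the table is bound to show excess harm from Dilapan-S. The documents do not support this. Nothing excludes misoprostol women or sets them to zero, and several provisions let their events be recorded. Reading 1 or reading 3 could equally be what was meant.
- A reader might infer a raised false-positive rate. That does not follow either. The rule of concluding a difference when a 95% interval excludes zero is in SAP 7.3, for secondary endpoints. SAP 7.4 is descriptive.

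The reply does not remove the gap. Permission to record an event is not a rule to count it alike in both arms, and the only classification the plan gives points the other way. The CRF is not among the documents, so actual capture under misoprostol cannot be settled here.

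**Conclusion.** The point holds as a misclassification with a practical consequence. Four events that either arm can have sit under a device-specific title, although the list is meant to compare Dilapan-S with misoprostol. Applied literally, the title leads to no comparison on those events or to unequal counting in an open-label trial.

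The effect runs from zero, if both arms are in fact scored alike, up to the full event rate, if scoring follows attribution completely. The upper end rests on equal true rates, complete attribution and rates that the documents do not supply. It describes displayed proportions, not a test error. The primary endpoint, the non-inferiority analysis and the sample size are untouched. The change is worth making because it improves a stated aim at little cost.

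**What to change.** In the SAP:

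- Move vaginal bleeding, membrane rupture, cervical laceration and analgesia need during ripening from 3.3.2 / Table 14.3.2 to 3.3.1 / Table 14.3.1.
- Report counts and proportions for both arms of the Safety population, regardless of attributed cause.
- For bleeding, analgesia need and membrane rupture, use one window in both arms, from the start of ripening to the end-of-ripening examination. Count any rupture other than planned amniotomy, so that rupture at insertion is kept.
- Count cervical laceration from the start of ripening through delivery in both arms.
- Keep vasovagal reaction at insertion, entrapment, fragmentation, retraction and failed insertion in 3.3.2 / Table 14.3.2, for Dilapan-S only. State the denominator for failed insertion, because the Safety population admits Dilapan-S women only if the device was inserted.

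The cost is a SAP and table-shell edit. The SAP already plans listings of pre-induction and delivery data (16.2.4.3 and 16.2.4.4). The downside is some chart re-check for misoprostol women if the CRF captured these items only in a device section.
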